8.1.3. Definitions of Baseline and Change from Baseline

The baseline will be defined as the last scheduled value recorded prior to dosing. If the date/time of the value is incomplete or missing, it will be excluded from the baseline calculation, unless the incomplete date/time indicates the value was recorded prior to dosing.

Individual changes from baseline will be calculated by subtracting the individual participant’s baseline value from the value at the postdose time point.

The summary statistics for change from baseline will be derived from individual participant’ values (eg, mean change from baseline will be the mean of the individual changes from baseline for all participants, rather than difference between the mean value at the postdose time point and mean value at baseline).

See Section 8.1.2 for more detail on handling unscheduled readings in the calculations.

8.2. Participant Disposition and Population Assignment

Participant disposition and population assignment will be listed.

A summary table by treatment will be provided, based on the safety population.

8.3. Screening Demographics and Baseline Characteristics

The screening demographics and baseline characteristics including age, sex, race, ethnicity, height, body weight, and body mass index will be listed.

A summary table by treatment will be provided, based on the safety population.

8.4. Prior and Concomitant Medication

Prior medication will be defined as medication that ends prior to dosing. Concomitant medication will be defined as medication that starts during or after dosing or starts but does not end prior to dosing.

Prior and concomitant medications will be coded using the WHO Drug Dictionary (version number is documented in the DMP). Prior and concomitant medications will be listed.

8.5. Pharmacokinetic Assessments

8.5.1. Pharmacokinetic Analysis

Noncompartmental methods applied with CCI to the serum concentrations of lebrikizumab will be used to determine the following PK parameters, when possible:

Parameter	Units	Definition
AUC(0-t _{last})	ng.h/mL	area under the concentration versus time curve from time zero to time t, where t is the last time point with a measurable concentration
AUC(0-∞)	ng.h/mL	area under the concentration versus time curve from time zero to infinity
%AUC(t _{last} -∞)	%	percentage of AUC that is due to extrapolation from the last measurable concentration to infinity
C _{max}	ng/mL	maximum observed drug concentration
t _{max}	h	time of maximum observed drug concentration
t _{1/2}	h	half-life associated with the terminal rate constant (λ_z) in non-compartmental analysis
CL/F	L/h	apparent total body clearance of drug calculated after extra-vascular administration
V _z /F	L	apparent volume of distribution during the terminal phase after extra-vascular administration
V _{ss} /F	L	apparent volume of distribution at steady state after extra-vascular administration

Additional PK parameters may be calculated, as appropriate. The software and version used for the final analyses will be specified in the CSR. Any exceptions or special handling of data will be clearly documented within the CSR.

CCI

General PK Parameter Rules

- Actual sampling times will be used in the final analyses of individual PK parameters, except for non-bolus pre-dose sampling times which will be set to zero. For non-bolus, multiple dose profiles, the pre-dose time will be set to zero unless a time

deviation falls outside of the protocol blood collection time window which is considered to impact PK parameter derivation.

- C_{max} and t_{max} will be reported from observed values. If C_{max} occurs at more than one time point, t_{max} will be assigned to the first occurrence of C_{max} .
- AUC parameters will be calculated using a combination of the linear and logarithmic trapezoidal methods (linear-log trapezoidal rule). The linear trapezoidal method will be applied up to t_{max} and then the logarithmic trapezoidal method will be used after t_{max} .
- The minimum requirement for the calculation of AUC will be the inclusion of at least 3 consecutive serum concentrations above the LLOQ, with at least 1 of these concentrations following C_{max} .
- AUC(0-∞) values where the percentage of the total area extrapolated is more than 20% will be flagged. Any AUC(0-∞) value excluded from summary statistics will be noted in the footnotes of the listing.
- $t_{1/2}$ will be calculated, when appropriate, based on the apparent terminal log-linear portion of the concentration-time curve. The start of the terminal elimination phase for each participant will be defined by visual inspection and generally will be the first point at which there is no systematic deviation from the log-linear decline in serum concentrations. $t_{1/2}$ will only be calculated when a reliable estimate for this parameter can be obtained comprising of at least 3 data points. If $t_{1/2}$ is estimated over a time window of less than 2 half-lives, the values will be flagged in the data listings. Any $t_{1/2}$ value excluded from summary statistics will be documented in the footnotes of the listing.
- A uniform weighting scheme will be used in the regression analysis of the terminal log-linear portion of the concentration-time curve.
- The parameters based on predicted last quantifiable drug concentration (C_{last}) will be reported.

Individual PK Parameter Rules

- Only quantifiable concentrations will be used to calculate PK parameters with the exception of special handling of certain concentrations reported below the limit of quantification (BLQ). Serum concentrations reported as BLQ will be set to a value of zero when all of the following conditions are met:
 - The compound is non-endogenous.
 - The samples are from the initial dose period for a participant or from a subsequent dose period following a suitable wash-out period.

- The BLQ concentration occurs before the first quantifiable concentration.
- All other BLQ concentrations that do not meet the above criteria will be set to missing.
- Also, where 2 or more consecutive concentrations are BLQ towards the end of a profile, the profile will be deemed to have terminated and therefore any further quantifiable concentrations will be set to missing for the calculation of the PK parameters unless it is considered to be a true characteristic of the profile of the drug.

Individual Concentration vs. Time Profiles

- Individual concentrations will be plotted utilizing actual sampling times.
- The terminal point selections will be indicated on a semi-logarithmic plot.

Average Concentration vs. Time Profiles

- The average concentration profiles will be graphed using scheduled (nominal) sampling times.
- The average concentration profiles will be graphed using arithmetic mean concentrations.
- The pre-dose average concentration for single-dose data from non-endogenous compounds will be set to zero. Otherwise, only quantifiable concentrations will be used to calculate average concentrations.
- Concentrations at a sampling time exceeding the sampling time window specified in the protocol, or $\pm 10\%$, will be excluded from the average concentration profiles.
- Concentrations excluded from the mean calculation will be documented in the final CSR.
- A concentration average will be plotted for a given sampling time only if two-thirds of the individual data at the time point have quantifiable measurements that are within the sampling time window specified in the protocol or $\pm 10\%$. An average concentration estimated with less than two-thirds but more than 3 data points may be displayed on the mean concentration plot if determined to be appropriate and will be documented within the final CSR.

Treatment of Outliers during Pharmacokinetic Analysis

Application of this procedure to all PK analyses is not a requirement. Rather, this procedure provides justification for exclusion of data when scientifically appropriate. This procedure describes the methodology for identifying an individual value as an outlier for potential

exclusion, but does not require that the value be excluded from analysis. The following methodology will not be used to exclude complete profiles from analysis.

Data within an Individual Profile

A value within an individual profile may be excluded from analysis if any of the following criteria are met:

- For PK profiles during single dosing of non-endogenous compounds, the concentration in a pre-dose sample is quantifiable.
- For PK profiles during multiple dosing, the concentration of the pre-dose sample exceeds all measured concentrations for that individual in the subsequent post-dose samples.
- For any questionable datum that does not satisfy the above criteria, the profile will be evaluated and results reported with and without the suspected datum.

Data between Individual Profiles

1. If there are fewer than 6 data points, then the dataset is too small to conduct a reliable range test. Data will be analyzed with and without the atypical value, and both sets of results will be reported.
2. If there are 6 or more data points, then an objective outlier test will be used to compare the atypical value to other values included in that calculation:
 - a. Transform all values in the calculation to the logarithmic domain.
 - b. Find the most extreme value from the arithmetic mean of the log-transformed values and exclude that value from the dataset.
 - c. Calculate the lower and upper bounds of the range defined by the arithmetic mean $\pm 3 \times \text{SD}$ of the remaining log-transformed values.
 - d. If the extreme value is within the range of arithmetic mean $\pm 3 \times \text{SD}$, then it is not an outlier and will be retained in the dataset.
 - e. If the extreme value is outside the range of arithmetic mean $\pm 3 \times \text{SD}$, then it is an outlier and will be excluded from analysis.

If the remaining dataset contains another atypical datum suspected to be an outlier, and there are still 6 or more data points following the exclusion, then repeat Step 2 above. This evaluation may be repeated as many times as necessary, excluding only 1 suspected outlier in each iteration, until all data remaining in the dataset fall within the range of arithmetic mean $\pm 3 \times \text{SD}$ of the log-transformed values.

Reporting of Excluded Values

Individual values excluded as outliers will be documented in the final CSR. Approval of the final CSR will connote approval of the exclusion.

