3. STUDY DESIGN

This is a Phase 1, participant- and investigator-blinded, randomized, placebo-controlled, single-dose study to investigate the safety, tolerability, and PK of lebrikizumab in healthy Chinese participants.

Approximately 24 healthy Chinese participants who have satisfied the entry criteria and completed all screening assessments will be enrolled to ensure at least 20 evaluable participants complete the study. Due to effect of body weight on PK, enrolment of participants with similar body weights between the cohorts is preferred. Participants will be assigned sequentially into 1 of 2 cohorts, each with 12 participants. Within each cohort, participants will be randomized in a blinded manner to lebrikizumab or placebo. The planned doses are as follows:

- Cohort 1: single 250 mg dose of lebrikizumab or placebo via SC injection (n=12; 10 lebrikizumab, 2 placebo)
- Cohort 2: single 500 mg dose of lebrikizumab or placebo via SC injection (n=12; 10 lebrikizumab, 2 placebo)

The duration of the study is approximately 21 weeks, and will consist of 3 periods:

- Screening period: Day -28 to Day -2
- Inpatient period: Day -1 to Day 8
 - single SC dose on Day 1
- Follow-up period: discharge until Day 120 ± 3 days.

Screening period

All participants will be screened within 28 days prior to enrollment.

Inpatient period

Eligible participants will be admitted to the CRU on Day -1. On Day 1, participants will be randomized, and will receive either lebrikizumab or placebo via SC injection.

Participants may be allowed to leave the CRU after completing assessments on Day 8, or later at the investigator's discretion.

[figure not shown]
Follow-up period

Participants will return for PK and immunogenicity sampling and safety assessments at predefined times up to approximately 120 days postdose.

Safety and tolerability will be assessed through safety laboratory assessments, 12-lead ECGs, vital sign measurements, recording of AEs, and physical examinations.

A schematic of the study design is presented in [Figure 1](#).

Figure 1: Study Design

Abbreviations: CRU = clinical research unit; ED = early discontinuation.

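### The SAP's between-profile outlier test uses a fixed 3-SD limit on a leave-one-out SD; if run on a clean set of 10 PK values, it labels a genuine value an outlier about 22% of the time

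*SAP*

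**What the plan says.** SAP section 8.5.1, under the heading on outliers between individual profiles, separates small from larger sets. With fewer than 6 values no test is run, and results with and without the atypical value are both reported. Otherwise: "If there are 6 or more data points, then an objective outlier test will be used to compare the atypical value" with the rest.

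The steps are:

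- 2a: "Transform all values in the calculation to the logarithmic domain".
- 2b: "Find the most extreme value from the arithmetic mean of the log-transformed values and exclude that value from the dataset".
- 2c: "Calculate the lower and upper bounds of the range defined by the arithmetic mean" plus and minus 3 SD of the remaining log values.
- 2d and 2e: keep the value if it lies inside the limits. If it lies outside, step 2e calls it an outlier that will be excluded.

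On repetition: "This evaluation may be repeated as many times as necessary, excluding only 1 suspected outlier in each iteration". A repeat requires another suspected value and at least 6 values still in the set.

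The opening paragraph of the same outlier section is softer. It says that the procedure need not be applied to every PK analysis, that it identifies values for possible exclusion, and that it does not oblige anyone to exclude them. It also bars using the method to remove complete profiles. Excluded values are documented in the CSR.

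The group sizes are in SAP section 3. Cohort 1 is a "single 250 mg dose of lebrikizumab or placebo via SC injection (n=12; 10 lebrikizumab, 2 placebo"), and Cohort 2 is a "single 500 mg dose of lebrikizumab or placebo via SC injection (n=12; 10 lebrikizumab, 2 placebo"). Protocol section 8.4.1 plans no assay of placebo samples, so a PK summary rests on at most 10 values per dose.

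**The concern.** A 3-SD limit suggests a rare event: about 0.27% for one normal value, or about 2.7% for at least one of 10. That reading does not fit this test, for two reasons. The value under test is the largest deviation of n, not one chosen at random. And the SD it is measured against has had that value taken out, so it is smaller and rests on only n-1 values. Both push the false-label rate up, most of all in small sets.

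Cmax, AUC(0-∞) and AUC(0-t_last) are the secondary endpoints, and SAP section 8.5.3 plans no inferential PK analysis, so the summary tables by treatment are the main PK result. If ordinary values are confirmed as outliers and dropped, those tables show too little between-participant variability and a shifted centre.

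**Working it through.** **Inputs.** n = 10 per dose (SAP section 3); smallest n for the test = 6; log scale; multiplier 3; SD from the n-1 remaining values (SAP section 8.5.1). For illustration only, a CV of 24.7%, the inter-individual variability of clearance in protocol section 2.2; the false-label rate does not depend on it. The plan states no error rate for the test, so there is no figure of its own to reproduce.

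**Formula.** For normal log values, the distance of a deleted value from the mean of the others, divided by their SD, equals sqrt(n/(n-1)) times a t variable with n-2 degrees of freedom. Summing over the n candidates bounds the chance that the most extreme one is labelled:

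rate ≤ n × P(|t with n-2 df| > 3 / sqrt(n/(n-1)))

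| n | 3 / sqrt(n/(n-1)) | two-sided tail, n-2 df | n × tail | simulated |
|---|---|---|---|---|
| 10 | 2.846 | 0.0216 | 21.6% | 21.6% |
| 8 | 2.806 | 0.0309 | 24.7% | 24.8% |
| 6 | 2.739 | 0.0520 | 31.2% | 31.2% |

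The simulation applied steps 2a to 2e literally to 1,000,000 clean normal sets per n.

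**Cause.** With the SD taken from all n values, the same limit of 3 labelled nothing at n=6 or n=10. It cannot, because the largest possible deviation in those units is (n-1)/sqrt(n), which is 9/3.162 = 2.846 at n=10. The high rate therefore comes from pairing a fixed 3 with the leave-one-out SD.

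**Effect on variability at n=10, if labelled values are dropped.**

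- Single pass: in flagged sets the SD falls on average to 0.669 of its full value, a fall of 33%. Over all clean sets: 0.216 × (1 - 0.669) = 7.1%.
- With repetition: in flagged sets it falls to 0.603. Over all clean sets: 0.216 × (1 - 0.603) = 8.6%. Two or more values are removed in 4.9% of sets.
- At a true CV of 24.7%, the mean geometric CV over all sets goes from 24.1% to 22.0% with repetition. In flagged sets it goes from about 24% to 16% on a single pass, and to 14.4% with repetition.
- In flagged sets the geometric mean moves by about 6% on a single pass. In 73% of them the removed value lay within 2.5 true SDs of the true mean.

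**Limits that hold a stated error rate.** Multiplier = t(1 - alpha/(2n), n-2) × sqrt(n/(n-1)), which is Grubbs' test in deleted form. At alpha = 0.05:

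- n=10: 3.833 × 1.054 = 4.04
- n=8: 4.115 × 1.069 = 4.40
- n=6: 4.851 × 1.095 = 5.31

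The simulated 95th percentiles of the test statistic were also 4.04, 4.40 and 5.31.

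**The case against.** The strongest reply is that the SAP does not run this test automatically. Someone must first regard a value as atypical, the procedure is optional, and its opening paragraph says exclusion is not required. The SAP promises no error rate, so 3 SD can be read as a screening threshold. All PK parameters are listed and exclusions are documented, so a reader could recalculate with all 10 values. The primary endpoint is safety.

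Much of this stands, and it rules out several stronger readings:

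- A reader might infer that 22% of this trial's PK summaries will lose a genuine value. The documents do not support that: 22% is the rate when a clean set is tested, and how often sets will be tested is not stated.
- A reader might take 31% as the working figure. It applies at n=6, which needs 4 of 10 values in a dose group to be missing. Protocol section 7.2 expects discontinuation to be uncommon, and dropouts may be replaced.
- A reader might see open-ended trimming in the repetition clause. Repetition stops once fewer than 6 values remain, so from 10 at most five could go.
- A reader might treat 33% as the overall bias. It describes flagged sets only; the average over all clean sets is 7% to 9%.
- A reader might accumulate the rate over three parameters and two doses. That needs correlations the documents do not give, and the two AUCs should be very close: sampling to Day 120 covers nearly five half-lives of about 25 days.

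What the reply does not do is repair the limit. The procedure exists to justify exclusions, and a test that confirms about one clean set of 10 in five is weak justification. Testing only sets where a value already looks odd selects those most likely to fail. Step 2e says a flagged value will be excluded, which does not agree with the opening paragraph. And at n of 6 or more the SAP asks only for documentation, not for both sets of results.

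**Conclusion.** The point holds conditionally. Applied to a clean log-normal set of 10, steps 2b to 2e label a genuine value an outlier about 22% of the time. If labelled values are dropped as step 2e states, the log SD is too small by about 33% in flagged sets on a single pass, and by about 7% (single pass) to 9% (with repetition) over all clean sets of 10.

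These figures assume independent log-normal values, no true outliers and every set tested. Heavier tails raise the rate: with t (5 df) on the log scale it was 35% at n=10. The realised effect depends on how often the test is used and whether labels are acted on, which the documents leave open. It touches only the descriptive secondary PK summaries, so this is an improvement to consider rather than a threat to the trial's conclusions.

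**What to change.** 1. In steps 2c to 2e and in the repetition clause, replace the fixed 3 × SD with t(1 - alpha/(2n), n-2) × sqrt(n/(n-1)) leave-one-out SDs, where n is the current number of values, and state alpha. At alpha = 0.05 the multipliers are 4.04 (n=10), 4.40 (n=8) and 5.31 (n=6). The choice of alpha is the sponsor's.
2. For n of 6 or more, report the PK summaries with and without any excluded value, as the SAP already does below 6. This alone would remove most of the harm, and it needs no choice of alpha.
3. Reconcile step 2e with the opening paragraph on whether a labelled value must be excluded.

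The cost is SAP wording, one line of code and a few extra summary rows, with no new data. The downside is that the statistic alone will flag fewer truly aberrant values; reporting both results keeps those values visible.

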8.5.2. Presentation of Pharmacokinetic Data

All PK parameters will be listed.

Arithmetic mean (+ SD) figures, overlaying individual figures, and individual figures by treatment and time postdose will be provided for serum PK concentrations. All figures will be produced on both linear-linear and linear-logarithmic scales. If required, this figure will be repeated using a subset of timepoints, which will be produced on the linear-linear scale only. The +SD bars will only be displayed on the linear-linear scale.

Summary tables by treatment will be provided for all PK parameters.

Exploratory graphical analyses relating lebrikizumab serum exposure and immunogenicity may be conducted.

8.5.3. Pharmacokinetic Statistical Methodology

No inferential statistical analyses are planned.

8.6. Safety and Tolerability Assessments

8.6.1. Adverse Events

All AEs will be coded using MedDRA (version number is documented in the DMP).

A pre-existing condition is defined as a condition that starts before the participant has provided written informed consent and is ongoing at consent. A non-treatment emergent AE is defined as an AE which starts after informed consent but prior to dosing. A TEAE will be defined as an AE that starts during or after dosing, or starts prior to dosing and increases in severity after dosing.

A treatment-related TEAE will be defined as a TEAE that is related to the study treatment, as determined by the investigator.

All AEs will be listed. In addition to the data recorded in the database, the listings will include derived onset time and duration. Onset time will be calculated from the time of dosing for TEAEs only.

The frequency of participants with TEAEs and the number of TEAEs will be summarized for the following categories:

- TEAEs (overall, serious, leading to discontinuation, and leading to death) by treatment
- TEAEs by severity and treatment
- Treatment-related TEAEs (overall, serious, leading to discontinuation, and leading to death) by treatment
- Treatment-related TEAEs by severity and treatment

The frequency of participants will be summarized separately for TEAEs and treatment-related TEAEs by the following:

- System organ class, preferred term, and treatment
- Preferred term and treatment

AEs of special interest will be listed separately and are the following for this study:

- conjunctivitis
- keratitis
- ISRs, and
- hypersensitivity reactions.

Conjunctivitis

Conjunctivitis events are AESI and will be identified using Customized MedDRA Query (CMQ) PTs (Table 1) nested within the following categories: Conjunctivitis and Keratitis.

The number and percentage of participants with at least 1 TEAE of conjunctivitis or keratitis will be summarized by treatment using MedDRA PT nested within categories (conjunctivitis and keratitis).

Table 2 - Search Criteria for Conjunctivitis and Keratitis

Conjunctivitis				Search Criteria Based on Selected PTs			
Narrow	Conjunctivitis	Conjunctivitis bacterial	Conjunctivitis viral				
Conjunctivitis CMQ	Conjunctivitis allergic	Atopic keratoconjunctivitis					

Keratitis	
High Level Term	Corneal infections, oedemas and inflammations
Preferred Term	Keratitis
	Atopic keratoconjunctivitis
	Allergic keratitis
	Ulcerative keratitis
	Vernal keratoconjunctivitis

Injection-site Reactions

For ISRs, events will be mapped to the MedDRA HLT of injection-site reactions, excluding PTs related to joint (the excluded PTs were determined by the most current MedDRA version):

- Injection site joint discomfort
- Injection site joint effusion
- Injection site joint erythema
- Injection site joint infection
- Injection site joint inflammation
- Injection site joint movement impairment
- Injection site joint pain
- Injection site joint swelling
- Injection site joint warmth

Hypersensitivity Reactions

The current standard MedDRA SMQs, published by MSSO, will be used to search for ISR events. The TEAEs are characterized as follows:

- Anaphylactic reaction SMQ (20000021; narrow, algorithm per SMQ guide, and broad)
- Hypersensitivity SMQ (20000214; narrow and broad), and
- Angioedema SMQ (20000024; narrow and broad).

Additional information on the AESIs described above may be found in the compound-level safety standards documentation.

For the AE data the following rules will apply:

- For the derivation of treatment-emergent status (applicable to all AEs): If the start date/time of an AE is incomplete or missing, an AE will be assumed to be a TEAE, unless the incomplete start date/time or the end date/time indicates an AE started before dosing.
- For the derivation of treatment-related status (applicable to TEAEs only): If the study treatment relationship for a TEAE is missing, a TEAE will be assumed to be a treatment-related TEAE.
- For the derivation of onset time (applicable to TEAEs only): If the start date/time of a TEAE is missing, onset time will not be calculated. If the start date/time of a TEAE is incomplete, where possible, the minimum possible onset time will be calculated and presented in ‘ \geq DD:HH:MM’ format (eg, if the date/time of dosing is 01MAY2019/08:00 and recorded start date/time of a TEAE is 03MAY2019, then the minimum possible onset time will be calculated by assuming a TEAE started at the first hour and minute of 03MAY2019 [03MAY2019/00:00], thus will be presented as onset time \geq 01:16:00 in the listing). If the start date of a TEAE is the same as the date of dosing but the start time of a TEAE is missing, an onset time will be presented as ‘ \geq 00:00:01’. Any clock changes will be accounted for in the derivation.
- For the derivation of duration (applicable to all AEs): If the end date/time of an AE is missing, duration will not be calculated. If the start or end date/time of an AE is incomplete, where possible, the maximum possible duration will be calculated and presented in ‘ \leq DD:HH:MM’ format (eg, if the start of an AE date/time is 01MAY2019/08:00 and its recorded end date/time is 03MAY2019, then the maximum possible duration will be calculated by assuming an AE ended at the last hour and minute of 03MAY2019 [03MAY2019/23:59], thus will be presented as duration \leq 02:15:59 in the listing). Any clock changes will be accounted for in the derivation.
- For the calculation of TEAE summary statistics: If the severity of a TEAE is missing, that TEAE will be counted under the ‘missing’ category.
- For the calculation of TEAE summary statistics: Where changes in severity are recorded in the eCRF, each separate severity of the AE will be reported in the listings, only the most severe will be used in the summary tables.

